5.3 Justification

The main objective of this study is to provide clinical data about the insertion procedure and the sensing quality of the BIOMONITOR III system. Clinical studies of the predecessor have shown that the concept of the implantable cardiac monitor is safe and efficient (see above). Prior to this first-in-man study the new insertion procedure of BIOMONITOR III was tested in an animal test study and in an insertion testing on deceased human bodies. The BIO|CONCEPT.BIOMONITOR III study will only be started, if both provided positive safety results.

The combination of a rigid and a flexible part, which yields a long sensing vector is a common design feature between BioMonitor 2 and BIOMONITOR III. Therefore the R-wave amplitude will be investigated as the main endpoint to confirm sensing quality. Since the main difference between BIOMONITOR III and BioMonitor 2 is in the insertion procedure, including the development of a new insertion tool set - the main focus of the study will be to assess insertion success and safety. Data from implantations and follow-ups are recorded in eCRFs, supplemented by clinical and device data collected through Home Monitoring. Home Monitoring allows for the reliable and continuous collection of many parameters directly as source data. By combining the Home Monitoring data with the clinical data from eCRFs, comprehensive information on BIOMONITOR III is available for analysis.

As the BIOMONITOR III system will be used for the first time in clinical routine a significant number of patients (up to 45 patients) and about 15 experienced investigators shall be included in this feasibility study. The open, uncontrolled design without study-specific procedures or device settings was chosen to minimize bias compared to a routine care population. To cover a broad patient population enrollment will not be restricted to any subgroup or indication. Furthermore, the in- and exclusion criteria are defined in a way to allow for the enrollment for an unselected, representative patient collective at the sites. . Since the study device is used in the intended way, the study does not impact on the device longevity.

Adverse Events which are related to the insertion procedure typically emerge within the first days after insertion. Therefore a total study duration of 4 weeks is deemed sufficient for safety follow-up. A 1-week in-office follow up will be complemented with a 1-month Home Monitoring observation and a patient interview via telephone to reveal all possible device or procedure – related events. Possible related SAEs of the patients will be followed up for an additional 4 weeks.

6 RISKS AND BENEFITS OF THE DEVICE AND CLINICAL INVESTIGATION

6.1 Anticipated clinical benefits

By participating in this study, the patient receives a modern device with many clinical benefits. In addition, they will benefit from being intensively supervised throughout the course of the study.

The benefit of the utilising of ICM's in the management of syncope is proven in many studies (e.g. EaSyAS⁶², ISSUE-2⁶³). With ICM's, diagnostic yield is improved compared to conventional testing⁶⁴⁻⁶⁸. This improved diagnostic accuracy translates into the delivery of more specific therapy^{14,15,69,70}. There is data to suggest that syncope burden can be reduced based on an early ICM based therapeutic decision^{14,64,70,71}. In addition, ICMs aid in establishing the diagnosis of AF^{40,48,72}. The use of ICMs for continuous cardiac rhythm monitoring has been shown to be superior to other means of ECG monitoring for AF screening in ischemic stroke patients⁷³. ICMs have also been successfully utilized in the assessment of various AF ablation therapies^{35,48,74}. The ultimate goal of AF monitoring will be to guide the clinical management of AF patients^{16,33,53}. For a patient with suspected AF who requires extensive monitoring of cardiac rhythm, the overall benefits provided by an ICM are greater than the limited disadvantages of over- or under-detection of AF.

Subjects who participate in this study might benefit from reduced noise level. Noise remains a significant problem amongst the current generation of ICMs. In a recent study⁷⁵ of a currently available ICM, only 55 percent of AF detections were confirmed as being AF. The large sensing vector of BIOMONITOR III is expected to yield a large QRS detected and reduce the degree of noise. This is expected to lead to a reduction in misdiagnoses and the improved performance of BIOMONITOR III's auto detection features.

6.2 Anticipated risks

6.2.1 Anticipated adverse device effects

Adverse device effects anticipated for patients with ICM implantation are described in section 18.7 of this clinical investigation plan. Since no additional procedures outside the clinical routine care are required during participation in BIO|CONCEPT.BIOMONITOR III, no further study-specific ADEs are anticipated.

Complications for patients and device systems generally recognized among practitioners also apply to BIOTRONIK devices. Primary sources of complication information include current scientific and technological knowledge.

6.2.2 Residual risks associated with the device

In principle, technical failures in the implant due to component failures, or other events that could compromise functioning, cannot be ruled out; they are expected to occur, however, very rarely. Instructions for use inform the users about hazardous usage conditions, but user errors cannot be prevented completely. There may be other risks associated with the devices that are currently unforeseeable.

6.2.3 Risk associated with participation in the study

Unauthorized access to the patient data or inadequate data protection (e.g. submission of non-pseudonymized data to the sponsor representatives) are possible risks associated with the participation. BIOTRONIK undertakes technical and organizational measures to protect data privacy and adheres to applicable European data protection laws.

Insertion of BIOMONITOR III does not differ significantly from the procedures applicable for comparable systems. Thus, no additional risks or burdens concerning device insertion derive from participation in the study.

6.2.4 Possible interactions with concomitant medical treatments

For the insertion of the BIOMONITOR III device, no interactions with concomitant medication or other medical treatment are expected.

The individual cardiovascular medication may have to be adapted to the patient's needs independent of the BIOMONITOR III device.

6.3 **Steps to control or mitigate the risks**

Risks associated with BIOMONITOR III which are mentioned above, as well as in section 18 have been reduced by special risk mitigation measures listed in the risk analysis of BIOTRONIK.

They are minimized through the utilization of strict aseptic technique, compliance with the technical manual, compliance with this clinical investigation plan and technical procedures, adhering to the guidelines for selection of patients, close monitoring of the patient's physiologic status during the procedures, and by promptly supplying BIOTRONIK with all pertinent information required by this clinical investigation plan.

Nevertheless, a residual risk remains.

6.4 **Risk-to-benefit rationale**

The benefit of the use of ICMs has been proven in different studies. It is important to point out that the physician will always have to weigh the benefits against rarely occurring complications on a case-by-case basis. In this case, the general risk/benefit analysis shows that the benefits for the patient clearly outweigh the risks.

Patients will benefit from the most advanced BIOTRONIK ICM technology. Patient monitoring mandated by the clinical investigation plan in the form of follow-ups and continuous observation via Home Monitoring ensures optimal patient care.

By participating in this study, patients contribute to medical progress which may benefit other patients in the future.

Most of the mentioned risks are associated with the general use of ICM systems and are not related to the study procedures.

We therefore conclude that benefits of this study outweigh the risks.

7 OBJECTIVES AND HYPOTHESES

7.1 Objectives

The objective of this study is to investigate the safety and efficacy of the new insertion procedure and the use and handling of the incision and insertion tools. Additionally, the sensing quality of the BIOMONITOR III will be investigated.

7.2 Endpoints and hypotheses

There are no pre-specified hypotheses and all analyses are explorative only.

7.2.1 Primary / secondary endpoint and hypotheses

Not applicable.

7.2.2 Data of interest

Information will be collected to characterize the insertion of the BIOMONITOR III and the safety and efficacy of the BIOMONITOR III system. The data will be statistically analyzed, where appropriate (see section 11). Specifically, the following data of interest will be analyzed:

- Insertion success rate
- R-wave amplitude measured at insertion and at 1 week / 1 month after insertion.
- Noise burden at 1-week follow-up and 1-month Home Monitoring observation
- Adverse events and device deficiencies associated with insertion procedure and insertion tools
- Remote Assistant trigger success rate
- Home Monitoring transmission success rate

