The shape of BIOMONITOR III allows placement in a parasternal position, which is closer to the heart than a typical pacemaker pocket and has been shown to result in increased amplitudes of the sensed cardiac signals.

The fractal coating of the electrodes, a low high-pass filtering and a lossless compression algorithm for the storage of the subcutaneous electrogram (sECG) provide for improved signal quality.

BIOMONITOR III continuously monitors the cardiac signal by detecting the R-waves and evaluating R-R intervals for arrhythmia detection:

After high-pass filtering of the cardiac input signal (to extinguish respiratory signals and baseline fluctuations), a second high-pass filter is applied to suppress T-waves and P-waves of the morphology/unfiltered signal. The resulting signal (sensing/filtered signal) is compared against an adaptive sensitivity threshold and R-waves get marked as sensed ventricular event (Vs) accordingly. In order to exclude artefacts from arrhythmia evaluation, a noise-window is (re-)started with every R-wave sense to reveal high-frequency artefacts. Those are marked as Vn and have an inhibitory effect on arrhythmia detection. Additionally, also signals which are considered too low in amplitude and thus most probably not of cardiac origin, are marked as Vn.

For recordings (device memory and transmissions via HomeMonitoring), the unfiltered signal is stored as it contains more information for diagnostic purposes, in particular P-waves.

During an in-office follow-up, both signal channels can be displayed simultaneously in real-time. The amplitudes of the unfiltered R-waves are measured automatically and annotated

beside the corresponding signals. Furthermore, daily means for R-wave amplitudes and percentage noise/day are stored as long-term trends.

The parameters for the sensing settings, such as sensing and high pass filter, sensing parameter sets (SensingConsult) etc. can be adjusted individually for each patient.

The sensing parameter sets are accessed via the feature SensingConsult. There are 5 preconfigured sensing programs addressing the most common signal challenges evolving from T/P-wave oversensing and signal amplitude variations due to VES.

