8.1.4.4 Insertion

After the insertion procedure the following information has to be entered in the respective eCRF:

- Date of insertion
- Serial number of BIOMONITOR III, CardioMessenger and Remote Assistant III
- Position and orientation of the BIOMONITOR III device
- Information on the insertion, handling of tools, including start time and end time of insertion procedure
- R-wave measurements (based on programmer screen)
- Device interrogation and provision of programmer download
- Adverse Event information
- Device Deficiency information

8.1.4.5 1-week follow-up

At the 1-week follow-up visit the following information has to be entered in the respective eCRF or provided via HMSC:

- Date of visit
- R-wave measurements (via HMSC)
- Noise rate measurements (via HMSC)
- P-wave visibility assessments
- Changes in device programming, if appropriate
- Device interrogation and provision of programmer download
- Adverse Event information
- Device Deficiency information

8.1.4.6 1-month Home Monitoring observation and telephone interview

The investigator is asked to consult the Home Monitoring Service Center (HMSC) one month after insertion and evaluate technical and diagnostic data. Additionally a telephone interview with the patient shall be conducted. The following information has to be entered in the respective eCRF or provided via HMSC:

- Dates of evaluated daily transmissions with periodic sECGs
- R-wave measurements (via HMSC)

- Noise rate measurements (via HMSC)
- P-wave visibility assessment
- Changes in device programming, if appropriate
- Answers given by the patient during the telephone interview
- Adverse Event information (based on a telephone interview with the patient)
- Device Deficiency information (based on a telephone interview with the patient)

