9 STUDY PROCEDURES

9.1 Overview

Subsequent to the enrollment and the insertion of the investigational device, one follow-up visit and a Home Monitoring observation one month after the insertion are scheduled. During all study visits designated BIOTRONIK employees who are appropriately trained on the subject matter are allowed to handle programmer data.

The visits and observations should take place within a certain time frame as listed in **Table 2**. This schedule should be followed as closely as possible. If circumstances prevent the presence of the patient at the follow-up visit, the reason for the missed follow-up has to be indicated on the respective eCRF.

Table 2: Overview of study procedures

	Enrollment / baseline	Insertion	1-week follow-up -2 days / +1 week	1-month Home Monitoring observation, telephone interview
Check inclusion / exclusion criteria	X			
Obtain informed consent	X			
Demographics, medical history, indication	X			
Insertion of BM III and assessment of insertion procedure and tool handling		X		
Interrogate BM III device and provide programmer data		X	X	
Program BM III with indication specific settings		X		
Program periodic subcutaneous ECG (cycle duration 1 day)		X		
Provide CardioMessenger and Remote Assistant, incl. test of Remote Assistant		X		
R-wave amplitude (based on programmer screen)		X		
R-wave amplitude (via HMSC)			X	X
Noise rate (via HMSC)			X	X
Assess P-wave visibility, based on periodic sECGs			X	X
Read-out of BM III data (RAM-dump)			X	
Restart statistics and recordings after read-out of BM III data			X	
Patient interview via telephone				X
Adverse Event and Device Deficiency reporting	X	X	X	X
Fill-in eCRFs	X	X	X	X

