9.3.2 Procedure after insertion

The following procedures shall be conducted after insertion:

- Interrogate the newly inserted BIOMONITOR III device.
- Freeze, store and print the sECG window and document the R-wave amplitude value on the insertion SDS. In case of varying amplitude labeling, document both, the lowest and the highest amplitude value (Figure 9 and Figure 10).

[figure not shown]

Figure 9: Freeze screen during interrogation

[figure not shown]

Figure 10: Document R-wave amplitude based on programmer screen or printout

- Program the BIOMONITOR III according to the clinical indication of the patient. Consider using the indication specific program settings (Go to 'Parameters' - 'Program sets' - 'Program consult', Figure 11)

[figure not shown]

Figure 11: Use 'ProgramConsult' for indication specific programming

- Program the Home Monitoring function to 'ON'

- Store the electronic procedure data (including final device settings, measurements) of the BIOTRONIK programmer. Provide the programmer data by uploading the PDF-File to the EDC-database (iMedNet) or by using the ReportShare-function (see 4.7.1.11). Alternatively, the PDF file can be send to the study e-mail address ([contact]).
- Register the patient at the Home Monitoring Service Center (HMSC).
- Activate a periodic sECG recording in the `Patient profile` tab of the HMSC (Go to `Remote scheduling`, press `edit` and select `daily`), Figure 12.

Configuration	
Remote Scheduling	 disabled  periodic  daily
Next HM follow-up	November 01 2018
Days between two HM follow-ups	91
HM follow-ups shall occur on	any day

Figure 12: Activate daily periodic sECG recording in HMSC

- Provide the Remote Assistant III to the patient and explain how to use the Remote Assistant III correctly. Let the patient trigger one sECG recording.
- Complete the insertion SDS and enter data in the insertion eCRFs in the iMedNet EDC database.
- Document any adverse event or device deficiency during the procedure by using the respective eCRF. Adhere to the reporting timelines listed in section 18.

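### The insertion R-wave reading is not directly comparable with the 1-week and 1-month values, and no scheduled visit records both methods

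*Protocol*

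**What the plan says.** Section 7.2.2 of the protocol names "R-wave amplitude measured at insertion and at 1 week / 1 month after insertion" as a single item among the data of interest. Section 5.3 gives the variable weight: "Therefore the R-wave amplitude will be investigated as the main endpoint to confirm sensing quality".

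The method differs by time point. In Table 2 (section 9.1) the row "R-wave amplitude (based on programmer screen" (closing bracket omitted) is marked at insertion only. The row "R-wave amplitude (via HMSC" (likewise) is marked at 1 week and 1 month only. Sections 8.1.4.4 to 8.1.4.6 repeat the split: "R-wave measurements (based on programmer screen" at insertion, HMSC at both follow-ups.

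Section 9.3.2 describes the insertion reading. The sECG window is frozen, stored and printed, and the labelled amplitude is written on the source data sheet: "In case of varying amplitude labeling, document both, the lowest and the highest amplitude value". At follow-up, sections 9.4 and 9.5 tell the investigator to inspect the HMSC trend values, which reach the database without an eCRF entry. Section 4.7.1.1 distinguishes the two displays. At an in-office follow-up, "The amplitudes of the unfiltered R-waves are measured automatically and annotated" in real time. Separately, "daily means for R-wave amplitudes and percentage noise/day are stored as long-term trends".

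**The concern.** Three time points listed as one item invite the reader to see one series. The first value is a momentary reading from a short screen window just after the procedure. The other two are trend values that, on the description in section 4.7.1.1, average over a day. A step between insertion and 1 week could be a real change in signal, or it could come only from the change of method. No scheduled pair of readings tells the two apart, and the protocol gives no conversion.

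A larger sample does not help, and neither does an analysis rule written later. If the paired reading is not collected, the offset cannot be estimated from the scheduled R-wave data.

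At stake is how the first point of the series is read. Section 5.3 makes this variable the main evidence on sensing quality, Table 1 in section 7.3 ties a promotional claim on R-wave sensing to it, and section 11.6 plans an interim analysis to support the launch decision. Section 11.3 also sets a p-value threshold of 0.05 for any comparison, so an insertion-to-follow-up test is not ruled out.

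**Working it through.** **Step 1. Set the sections side by side.** The protocol states no figure for this point, so there is nothing of its own to reproduce.

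| Time point | Scheduled R-wave source | Nature of the value | Section |
|---|---|---|---|
| Insertion | Programmer screen | Label in a frozen window; lowest and highest if labels vary | 8.1.4.4, 9.1, 9.3.2 |
| 1 week | HMSC | Trend value | 8.1.4.5, 9.1, 9.4 |
| 1 month | HMSC | Trend value, same source as at 1 week | 8.1.4.6, 9.1, 9.5 |

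That the HMSC trend value is the daily mean is an inference from sections 4.7.1.1 and 9.4 read together. No single sentence says so.

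**Step 2. Write out each contrast.** Let b be the systematic difference, HMSC value minus programmer value, taken as constant over time.

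- Insertion to 1 week, or insertion to 1 month: observed change = true change + b. The two terms cannot be separated.
- 1 week to 1 month: observed change = (value at 1 month + b) − (value at 1 week + b) = true change. The offset cancels.
- Daily HMSC values from shortly after insertion: section 9.3.2 has Home Monitoring switched on and the patient registered after insertion, and section 4.7.1.11 describes a daily device message. This course also uses one method, so b cancels.

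**Step 3. Illustrate what an offset could do.** Neither b nor the standard deviation (SD) of the paired differences is in the protocol; both are assumed below. Take n = 45, true change 0 and a two-sided 5% normal test of zero mean paired change. With SE = SD/√45,

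P(p < 0.05) = Φ(b/SE − 1.96) + Φ(−b/SE − 1.96).

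| Assumed SD (mV) | SE (mV) | 95% half-width (mV) | b = 0.05 mV | b = 0.10 mV |
|---|---|---|---|---|
| 0.1 | 0.015 | 0.029 | 92% | > 99% |
| 0.2 | 0.030 | 0.058 | 39% | 92% |
| 0.3 | 0.045 | 0.088 | 20% | 61% |

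With b = 0 each entry would be 5%. For scale, the predecessor 1-week means in sections 5.2.1 and 5.2.2 are 0.7 and 0.75 mV, so 0.05 mV is about 7% of the amplitude (0.05/0.75 = 0.067) and 0.10 mV about 13% (0.10/0.75 = 0.133). Nothing in the protocol says whether an offset of that size exists.

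**The case against.** The strongest reply is that the plan needs no bridge. Section 7.2 states that there are no hypotheses and that all analyses are explorative, section 8.1.3 defines no statistical endpoints, and section 11.1 is mainly descriptive. No change from insertion is specified anywhere, and how the visits are presented is normally left to the statistical analysis plan. Both methods are openly labelled in Table 2. A check straight after the procedure cannot use a daily mean, because no day of data exists yet. All of this stands, and it limits the weight of the point.

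A reader might infer three stronger things, none of which the documents support.

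- *That the whole course after insertion is confounded with the method.* It is not. The 1-week and 1-month values share a source, and daily HMSC values begin shortly after insertion. Only the insertion reading stands apart.
- *That comparison with the predecessor is spoiled.* The predecessor means quoted are 1-week values, and this study has its own 1-week value to set beside them. The protocol nowhere plans to use the insertion value for that purpose.
- *That no bridging data can exist.* At 1 week the device is interrogated, the programmer data including measurements are stored and provided, and the device memory is read out (sections 9.4 and 9.7). The protocol does not say whether these files hold a programmer R-wave reading. What can be said is that none is scheduled or recorded as such.

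The reply does not make the insertion value comparable with the later ones, and an analysis plan alone cannot ensure a matching reading.

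**Conclusion.** The point holds in a narrow form. The insertion R-wave amplitude is not directly comparable with the 1-week and 1-month values, no scheduled visit records both, and any insertion-to-follow-up difference mixes true change with an offset of unknown size. The course from shortly after insertion to 1 month is unaffected, provided any offset is stable and the daily transmissions arrive.

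The size cannot be taken from the protocol. The probabilities above rest wholly on assumed offsets and SDs and show only that a modest offset could pass for a change. The conclusion also rests on reading the HMSC trend value as the daily mean. Because the study is exploratory and specifies no change-from-insertion analysis, no stated result is wrong. This is a low-cost improvement worth considering.

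**What to change.** In Table 2 and section 9.4, schedule the programmer-screen R-wave reading at the 1-week visit as well, using the same freeze-and-record step as section 9.3.2, with lowest and highest values if the labels vary. Add the matching item to section 8.1.4.5. Then:

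- report insertion to 1 week from programmer pairs only;
- report the later course from HMSC daily values only;
- give the 1-week programmer-minus-HMSC difference, with its confidence interval, as the method offset.

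If no reading is added, state in section 7.2.2 that the insertion value comes from a different method, report it separately, and describe the course from HMSC values alone.

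The cost is one or two more values on the 1-week source data sheet and eCRF, taken at an interrogation that already takes place. The fallback needs only a wording change.
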